**Table 5: Sensitivity Estimators of the Primary Efficacy Endpoint**

Estimator	Approach for Intercurrent Events	Imputation Method	Analytical Method
Sensitivity Estimator 1	Observed ALSFRS-R total score collected up to Week 24 will be included in the analysis and missing data will not be imputed.	Not applicable.	MMRM described in Section 8.6.1 .
Sensitivity Estimator 2	All missing ALSFRS-R total score, regardless of which intercurrent event causes data missing, will be imputed under a MAR paradigm.	Imputation will be performed for each randomized treatment group and will include the following factors in the model: ALSFRS-R total score at previous visits including baseline, riluzole use at baseline, and edaravone use at baseline.	ANCOVA model with ALSFRS-R total score change from baseline to Week 24 as the response variable. The model terms will include treatment group, baseline ALSFRS-R total score, riluzole use status at baseline and edaravone use status at baseline.
Sensitivity Estimator 3	For both reldesemtiv and placebo groups, missing ALSFRS-R total score will be imputed based on the distribution of the placebo group.	For each treatment group, missing ALSFRS-R total scores will be imputed using the parameters from the imputation model of the placebo distribution. The following terms will be included in the imputation model: ALSFRS-R total score at previous visits including baseline, riluzole use at baseline, and edaravone use at baseline.	ANCOVA model with ALSFRS-R total score change from baseline to Week 24 as the response variable. The model terms will include treatment group, baseline ALSFRS-R total score, riluzole use status at baseline and edaravone use status at baseline.
Sensitivity Estimator 4	For reldesemtiv group, tipping point analyses will be conducted by setting the imputed values for the deaths successively worse (starting from 5% worse and with an increment of 5% worse for each of the next step) until a reverse result is obtained. ( Ratitch 2013 ). For reasons of missing other than deaths, missing data will be	For reldesemtiv group, an increment of 1 for the range of shift parameters that reverses the study result will be applied in the multiple imputation.  For placebo group, the imputation will be performed with the following factors included in the imputation model: ALSFRS-R total score from previous	ANCOVA model with ALSFRS-R total score change from baseline to Week 24 as the response variable. The model terms will include treatment group, baseline ALSFRS-R total score, riluzole use status at baseline and edaravone use status at baseline.

Estimator	Approach for Intercurrent Events	Imputation Method	Analytical Method
	
imputed with MAR-based imputed values.
 
For placebo group, missing ALSFRS-R total score will be imputed with MAR-based imputed values.
	
visits including baseline, riluzole use at baseline, and edaravone use at baseline.
	

Sensitivity Estimator 5
	
For reldesemtiv group, tipping point analyses will be conducted by setting the imputed values for all missing data, regardless of reasons of missing, successively worse (starting from 5% worse and with an increment of 5% worse for each of the next step) until a reverse result is obtained (Ratitch 2013).
 
For placebo group, missing ALSFRS-R total score will be imputed with MAR-based imputed values.
	
For reldesemtiv group, an increment of 1 for the range of shift parameters that reverses the study result will be applied in the multiple imputation.
 
For placebo group, the imputation will be performed with the following factors included in the imputation model: ALSFRS-R total score from previous visits including baseline, riluzole use at baseline, and edaravone use at baseline.
	
ANCOVA model with ALSFRS-R total score change from baseline to Week 24 as the response variable. The model terms will include treatment group, baseline ALSFRS-R total score, riluzole use status at baseline and edaravone use status at baseline.


Sensitivity Estimator 6 (COVID-19 related)
	
Data collected after the occurrences of COVID-19 related intercurrent events will be excluded.
	
After excluding the data that were collected after the occurrences of COVID-19 related intercurrent events, imputation will be performed for each randomized treatment group and including the following factors in the imputation model: ALSFRS-R total score from previous visits including baseline, riluzole use at baseline, and edaravone use at baseline.
	
ANCOVA model with ALSFRS-R total score change from baseline to Week 24 as the response variable. The model terms will include treatment group, baseline ALSFRS-R total score, riluzole use status at baseline and edaravone use status at baseline.

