Approximately 740 patients will be screened in order to randomize/enroll approximately 555 patients, such that approximately 444 evaluable patients complete the 24-week of double-blind period of the trial.

Key Eligibility Criteria:

A full listing of eligibility criteria can be found in [Section 5](#). Patients are eligible to be included in the trial only if all criteria are met.

Key Inclusion Criteria

- Males or Females between the ages of 18 and 80 years of age, inclusive
- Diagnosis of familial or sporadic ALS (defined as meeting the laboratory-supported probable, probable, or definite criteria for ALS according to the World Federation of Neurology El Escorial criteria published in 2000 [[Brooks 2000](#)]). Patients who meet the possible criteria are eligible if they have lower motor neuron findings; those who have purely upper motor neuron findings are ineligible.
- First symptom of ALS \leq 24 months prior to screening. The qualifying first symptoms of ALS are limited to manifestations of weakness in extremity, bulbar, or respiratory muscles. Cramps, fasciculations, or fatigue should not be taken in isolation as a first symptom of ALS.
- ALSFRS-R total score \leq 44 at screening. Patients with a total score of 45 or higher may be rescreened 60 ± 7 days following the original screening date and be deemed eligible if their ALSFRS-R total score is \leq 44 or if their score is 2 or more points less than at initial screening. Such patients must continue to meet all other inclusion/exclusion criteria at the time of rescreening.
- Upright FVC \geq 65.0% of predicted for age, height, sex and ethnicity at screening according to Global Lung Initiative equation
- Able to perform reproducible pulmonary function tests defined as being able to perform FVC at screening with variability of the 2 highest raw values of less than 10% with a maximum of 5 trials permitted. Screening FVC results must be reviewed and approved by the central review process prior to randomization.
- Must be either on riluzole for \geq 30 days prior to screening or have not taken it for at least 30 days prior to screening

- Must have completed at least 2 cycles of edaravone at the time of screening or have not received it for at least 30 days prior to screening
- Able to swallow whole tablets at the time of screening

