9.2. Sample Size Determination

With a 2:1 randomization ratio to reldesemtiv and placebo groups, respectively, a sample size of approximately 555 patients is required to achieve at least 90% power to detect a 1.8 point treatment difference between reldesemtiv and placebo in the change from baseline to Week 24 in ALSFRS-R total score. This calculation is based on a two-sample t-test with two-sided alpha at 0.05 level, a common standard deviation (SD) of 5.5 points, and accounting for missing data and early treatment termination.

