## 8.5. Multiple Comparisons and Multiplicity

The null hypothesis for the primary and secondary efficacy endpoints will be tested in a prespecified order using a closed testing procedure. This procedure will maintain the family-wise error rate at two-sided significance level of 0.0499 for all primary and secondary hypotheses tested in a confirmatory sense. The testing steps are described as follows:

- Step 1: The null hypothesis for the primary endpoint  $H_{01}$  is that there is no treatment difference in the change from baseline to Week 24 in ALSFRS-R total score between patients randomized to placebo and those randomized to reldesemtiv in the FAS. The hypothesis will be tested at the two-sided significance level of 0.0499. If this hypothesis is rejected, testing will proceed to Step 2; otherwise testing will stop.
- Step 2: The null hypotheses for the first secondary endpoint  $H_{02}$  is that the Mann-Whitney probability of a more favorable status in reldesemtiv or placebo group in the FAS is 0.5. The status is quantified by joint ranks based on the combined assessment of change in ALSFRS-R total score, time to onset of respiratory insufficiency, and survival time up to Week 24. The hypotheses will be tested at the two-sided significance level of 0.05. If this hypothesis is rejected, testing will proceed to Step 3; otherwise testing will stop.
- Step 3: The null hypotheses  $H_{03}$  is that there is no treatment difference in change from baseline to Week 24 in the percent predicted FVC between patients randomized to placebo and those randomized to reldesemtiv in the FAS. The hypotheses will be tested at the two-sided significance level of 0.05. If this hypothesis is rejected, testing will proceed to Step 4; otherwise testing will stop.
- Step 4: The null hypotheses  $H_{04}$  is that there is no treatment difference in change from baseline to Week 24 in the ALSAQ-40 total score between patients randomized to placebo and those randomized to reldesemtiv in the FAS. The hypotheses will be tested at the two-sided significance level of 0.05. If this hypothesis is rejected, testing will proceed to Step 5; otherwise testing will stop.

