### **8.6.1.1. Imputation of the Missing Data for the Primary Efficacy Analysis**

The extent of missing data and the pattern of missing data reasons will be tabulated. Missing ALSFRS-R total score will be imputed for the primary efficacy analysis described in [Section 8.6.1](#). For each randomized treatment group, the missing data will be filled sequentially starting at the earliest time point and progressing until the last time point based on a multivariate joint normal imputation model ([Schafer 1997](#)). The imputation model will include the following terms: ALSFRS-R total score at previous visits including baseline (in reldesemtiv or placebo group), riluzole use and/or edaravone use at baseline, and other covariates selected using stepwise regression for the primary analysis (see [Section 8.6.1](#)) such as pre-study disease progression rate, age and/or baseline percent predicted FVC. Fifty set of complete data will be generated for analysis to produce 50 sets of estimates. Rubin's imputation rules ([Rubin 1987](#)) will be used to combine the LSM estimates of the treatment difference, 95% confidence interval and p-value. The example SAS code can be found in [Section 12.5](#).

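### If stepwise selection keeps any baseline covariate, Sensitivity Estimators 2–6 leave it out, so the tipping-point search starts from a slightly different analysis than the primary one

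*SAP*

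**What the plan says.** **Primary analysis.** SAP 8.6.1 and Table 4 give an MMRM with treatment, visit, baseline ALSFRS-R, riluzole use, edaravone use, and by-visit interactions for baseline score and treatment only. Covariates retained by stepwise selection (entry 0.25, stay 0.1, on blinded data) are added. The candidates are pre-study progression rate, age and baseline percent predicted FVC. The imputation in SAP 8.6.1.1 uses earlier scores, riluzole, edaravone "and other covariates selected using stepwise regression for the primary analysis".

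**Sensitivity analyses.** In SAP Table 5, only Estimator 1 keeps the 8.6.1 model. Estimators 2–6 use a Week 24 ANCOVA: "The model terms will include treatment group, baseline ALSFRS-R total score, riluzole use status at baseline and edaravone use status at baseline". The imputation terms for Estimators 2, 3 and 6 are earlier scores, riluzole and edaravone. For Estimators 4 and 5 the same terms are listed for the placebo group only; none are listed for reldesemtiv. The tipping-point analyses start at 5% worse and continue in 5% steps "until a reverse result is obtained". Protocol 9.4.2 and SAP 6.8.1 name ANCOVA with MAR-based multiple imputation, which is Estimator 2, as their base.

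**First secondary endpoint.** SAP 8.7.1.1 imputes as in 8.6.1.1, so with the selected covariates. Table 6 lists imputation terms without them for Estimators 8 and 10, and for the placebo group of Estimator 9.

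**The concern.** These estimators are meant to show whether the primary result survives other assumptions about missing data. That is cleanest when nothing else changes. Here the covariate set changes as well, in both the imputation and the analysis model, and the SAP gives no reason. It looks like an oversight, because the fallback ANCOVA for subgroups in SAP 8.4.1 does carry the covariates identified before database lock.

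Estimator 2 still assumes MAR, but conditional on fewer variables, and its analysis model is less precise if the omitted covariates are prognostic. A primary result just under 0.0499 could therefore be non-significant in Estimator 2, before any shift is applied. The SAP has no rule for that case, and a reader could blame missing data for what a dropped covariate did.

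**Working it through.** **Inputs from the documents.** Allocation is 2:1 in favour of reldesemtiv. Protocol 9.2 states that "a sample size of approximately 555 patients is required to achieve at least 90% power to detect a 1.8 point treatment difference". The t-test behind that figure assumes "two-sided alpha at 0.05 level, a common standard deviation (SD) of 5.5 points". Protocol 1.1 expects that "approximately 444 evaluable patients complete the 24-week of double-blind period of the trial". For the final primary test, SAP 8.5 says: "The hypothesis will be tested at the two-sided significance level of 0.0499".

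**Assumed.** R², the share of residual Week 24 variance explained by the omitted covariates, is not in the documents; 5–20% is used here. A true effect of 1.2 points is used as a less favourable case than the design value of 1.8.

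**1. The plan's own figure.** Placebo n = 1.5 × (1.960 + 1.282)² × 5.5² / 1.8² ≈ 147.2, so 148. With 296 on reldesemtiv the total is 444, and 444 / 0.80 = 555. The plan's sample size reproduces. SE = 5.5 × √(1/148 + 1/296) = 0.5537.

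**2. Upper bound.** If the primary adjusted fully for the covariates at Week 24, dropping them would multiply the SE by 1/√(1 − R²). The critical value at 0.0499 is 1.9608. At the same point estimate, the base is non-significant once the primary p exceeds 2 × [1 − Φ(1.9608/√(1 − R²))].

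| R² | SE ratio | Primary p above which the base is non-significant |
|---|---|---|
| 5% | 1.026 | 0.0442 |
| 10% | 1.054 | 0.0387 |
| 15% | 1.085 | 0.0334 |
| 20% | 1.118 | 0.0284 |

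**3. The plan as written.** Selected covariates enter the MMRM as main effects, without a by-visit term, so most of the Week 24 precision gain is lost. This was simulated with 555 patients, 2:1 allocation, about 17% missing at Week 24 under MAR, 50 imputations per arm and 600 trials per cell. The primary had the covariate in the MMRM and the imputation; Estimator 2 had it in neither.

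| R² | SE ratio, base/primary | Base non-significant given primary significant, effect 1.8 | Same, effect 1.2 |
|---|---|---|---|
| 0 | 0.998 | 0.5% | 2.4% |
| 10% | 1.014 | 1.4% | 2.1% |
| 20% | 1.033 | 1.4% | 6.0% |

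Monte Carlo error is about 0.3–1.2 percentage points. The R² = 0 row shows that the switch from MMRM to ANCOVA matters little by itself.

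Thresholds at the same point estimate:
- R² = 10%: 1.9608 × 1.014 = 1.988, p ≈ 0.047.
- R² = 20%: 1.9608 × 1.033 = 2.026, p ≈ 0.043.

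**4. Would adding the covariates to the ANCOVA restore a match?** No. A Week 24 ANCOVA adjusts fully at Week 24, while the main-effect MMRM does not. A complete-data simulation (1,000 trials per cell, covariate effect growing linearly with time) gave base/primary SE ratios of 1.015 and 1.032 as written at R² = 10% and 20%, but 0.963 and 0.925 after that edit. Arithmetic agrees: √0.90 × 1.015 = 0.963 and √0.80 × 1.032 = 0.923. At a true effect of 1.2, trials with a significant base and a non-significant primary rose from about 0.3% to 5.8–9.1% over R² of 10–20%.

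**The case against.** The strongest reply is that the plan already supplies the right comparison. Estimator 2 is reported separately and is the zero-shift point, so a non-significant base would be visible as a non-significant MAR analysis. Estimators 3–5 use the same ANCOVA terms, so against Estimator 2 they do isolate the missing-data assumption. Estimator 1 keeps the primary MMRM. A fixed covariate set is also a fair check on a model whose covariates are chosen from the data, and the confirmatory sequence in SAP 8.5 does not use these estimators.

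All of that stands. It limits the point to reading Estimators 3–5 against the primary result, which is the result they are there to support.

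A reader might infer more than the documents bear:
- That every estimator changes the missing-data assumption, the imputation and the analysis model together. Estimator 2 remains MAR, and for Estimators 4 and 5 the reldesemtiv imputation terms are simply not stated.
- That the mismatch is certain. It arises only if selection keeps at least one candidate.
- That primary p-values as low as 0.028 are exposed. That needs full Week 24 adjustment in the primary MMRM, which SAP 8.6.1 does not specify.

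**Conclusion.** The mismatch is in the text, and its effect is modest. If a covariate is selected, the tipping-point base differs from the primary by model as well as by the variables on which MAR is conditioned. With R² of 10–20%, the base SE is about 1–3% larger. A primary p between about 0.047 (R² = 10%) or 0.043 (R² = 20%) and 0.0499 could then be non-significant at zero shift. Among trials with a significant primary result, that happened in about 1.4% at the design effect, against 0.5% with no covariate effect. At an effect of 1.2 there was no detectable excess at R² = 10%, and 6.0% against 2.4% at R² = 20%.

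These figures rest on the assumed R² and on the simulated missingness and covariate pattern. The sample size, the alpha and the confirmatory test are unaffected. This is a nearly free improvement in interpretability and does not threaten the primary conclusion.

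**What to change.** 1. In Table 5 (Estimators 2–6) and Table 6 (Estimators 8–10), use the 8.6.1.1 imputation terms, including the selected covariates. State them for the reldesemtiv arm in Estimators 4, 5 and 9.
2. Analyse Estimators 2–6 with the 8.6.1 MMRM, so that zero shift reproduces the primary result. Estimator 2 then coincides with the primary and serves as the zero-shift row. Because Protocol 9.4.2 names ANCOVA as the base, record the change in the SAP. If ANCOVA is kept, add the selected covariates to it and also add covariate-by-visit terms to the primary MMRM; do not make the ANCOVA edit alone.
3. Align the prototype code in SAP 12.5. Item 1 omits the selected covariates from the primary MMRM. Items 2 and 4 omit them from the imputation, and also omit baseline ALSFRS-R, which the text includes.

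The cost is a few phrases in two tables and some code edits. Sample size and alpha do not change. The work can be done blinded before database lock, which is the limit SAP section 2 sets for decisions on the final analysis.

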## 8.7. Analysis of the Secondary Efficacy Endpoints

The secondary endpoint(s) of the trial are:

- Combined assessment of change in ALSFRS-R total score, time to dependence on assisted ventilation (either invasive or non-invasive), and survival time up to Week 24
- Change from baseline to Week 24 in the percent predicted FVC
- Change from baseline to Week 24 in the ALSAQ-40 total score
- Change from baseline to Week 24 in handgrip strength (average of both hands)

The analyses of the secondary endpoints are described in [Sections 8.7.1](#), [8.7.2](#) and [8.7.3](#).

### 8.7.1. Analysis of the First Secondary Efficacy Endpoint

The estimand of the first secondary endpoint (combined assessments of change in ALSFRS-R total score, time to dependence on assisted ventilation (either invasive or non-invasive), and survival time up to Week 24) is the stratified Mann-Whitney probability of a more favorable status in the reldesemtiv group compared to the placebo group in the FAS, based on the joint ranks of the combined assessments collected up to Week 24, and accounting for the intercurrent events of death, dependence on assisted ventilation (either invasive or non-invasive) and decline in ALSFRS-R total score. Dependence on assisted ventilation is defined as patients using invasive or non-invasive ventilation for  $\geq 22$  hours per day for  $\geq 10$  consecutive days.

The joint rank comparison method developed by Berry et al. ([Berry 2013](#)) will be applied for the first secondary endpoint. Each patient will first be compared with all others in the analysis population in a pairwise manner on their combined assessments. A score of +1, 0 or -1 will be assigned if one has better, tie or worse outcome than the other, respectively. The worst rank is assigned to patients who die during the trial, followed by ranking on severity of the health status for patients who survive according to their dependence on assisted ventilation and ALSFRS-R total score. The ranking hierarchy is listed as follows:

- Patients who died rank worse than patients who survived.
  - Patients who died earlier rank worse than patients who died later.
- Being dependent upon assisted ventilation is likely to permit patients to survive longer and who would have otherwise died without the intervention. Thus, patients who met the definition of dependence on assisted ventilation (either invasive or non-invasive) rank better than those who died, but worse than those who did not meet the definition of dependence on assisted ventilation (either invasive or non-invasive), regardless of whether the decline in ALSFRS-R total score is smaller or not.
  - Among patients who survived but dependence on assisted ventilation (either invasive or non-invasive), patients with the dependence earlier rank worse.
- Among patients who survived and without dependence on assisted ventilation (either invasive or non-invasive), patients with greater decline in ALSFRS-R total score from baseline rank worse.

- For patients who discontinued early, comparison is based on the last time-point measurements that are both available for the patients in pairs.
- If it is not possible to assign either patient as having the better outcome, then the score assigned to the pair is 0.

For each patient, the assigned scores (+1, -1 or 0) from the pairwise comparisons with all others will be summed, then all patients in the FAS will be ranked according to their summed scores to create a rank score from 1 for the lowest possible summed score to N (total number of patients in the analysis population) for the highest possible summed score. If ties occur, each of the tied summed scores will be assigned the average of the ranks the tied summed scores would have if there were no ties.

A stratified Wilcoxon test will be applied to compare the standardized joint ranks between reldesemtiv and placebo groups (as ranks divided by pooled group sample size plus one) adjusting for baseline riluzole use and baseline edaravone use. The win probability, win ratio, van Elteren (or stratified Wilcoxon) test statistic, and p-value will be presented.

In the event that mortality rate up to week 24 is higher than expected, the first secondary endpoint may be considered as the primary efficacy endpoint before database lock for the Week 24 primary analysis.

